7.3.5 General Guidance for Hematology Toxicity and Dose Modification

Hematologic toxicities including neutropenia, leukopenia, anemia, and thrombocytopenia have been observed in patients treated with abemaciclib, and causality has been established. Severe (Grade 3 and 4) neutropenia was observed in patients receiving abemaciclib. Patients should be monitored closely for signs of infection, anemia, and bleeding. **The following instructions from Table 7-5 must be used to manage hematologic toxicities.**

Table 7-5: Dose Modification and Management — Hematologic Toxicities

Monitor complete blood counts prior to the start of abemaciclib therapy, every 2 weeks for the first 2 months, monthly for the next 2 months, and as clinically indicated.	
CTCAE Grade	Abemaciclib Dose Modifications
Grade 1 or 2	No dose modification is required.
Grade 3	Suspend dose until toxicity resolves to \leq Grade 2. Dose reduction is not required.
Grade 3, recurrent, or Grade 4	Suspend dose until toxicity resolves to \leq Grade 2. Resume at next lower dose.
Patient requires administration of a blood cell growth factor	Suspend abemaciclib dose for at least 48 hours after the last dose of blood cell growth factor and until toxicity resolves to \leq Grade 2. Resume abemaciclib at next lower dose unless the dose was already reduced for the toxicity that led to the use of the growth factor.

7.3.6 General Guidance for Nonhematologic Toxicities (excluding diarrhea, increased ALT and ILD/Pneumonitis) Monitoring

Nonhematologic toxicities excluding diarrhea

- Grade 1 or 2: No dose modification is required.
- Persistent or recurrent Grade 2 toxicity that does not resolve with maximal supportive measures within 7 days to baseline or Grade 1: suspend dose until toxicity resolves to baseline or Grade 1. Resume at next lower dose.
- Grade 3 or 4: suspend dose until toxicity resolves to baseline or Grade 1. Resume at next lower dose.

Table 7-6: Dose Modification and Management — Nonhematologic Toxicities Excluding Diarrhea, ALT/AST Increased, and ILD/Pneumonitis

CTCAE Grade	Abemaciclib Dose Modifications
Grade 1 or 2	No dose modification is required.
Persistent or recurrent Grade 2 toxicity that does not resolve with maximal supportive measures within 7 days to baseline or Grade 1	Suspend dose until toxicity resolves to baseline or Grade 1. Resume at next lower dose.
Grade 3 or 4	

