7.3.2 General Guidance for Increases in Serum Creatinine and Assessment of Renal Insufficiency

Abemaciclib has been shown to increase serum creatinine due to inhibition of renal tubular transporters without affecting glomerular function (as measured by iohexol clearance). In clinical studies, increases in serum creatinine occurred within the first month of abemaciclib dosing, remained elevated but stable through the treatment period, were reversible upon treatment discontinuation, and were not accompanied by changes in markers of renal function, such as blood urea nitrogen (BUN), cystatin C, or calculated glomerular filtration rate based on cystatin C.

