Serology	Acetaminophen protein adducts
Hepatitis A virus (HAV) testing:	Alkaline phosphatase isoenzymes
HAV total antibody	Ceruloplasmin
	Copper
	Ethyl alcohol (EtOH)
	Haptoglobin
	Immunoglobulin IgA (quantitative)
	Immunoglobulin IgG (quantitative)
	Immunoglobulin IgM (quantitative)

HAV IgM antibody	Phosphatidylethanol (PEth)
Hepatitis B virus (HBV) testing:	Urine Chemistry
Hepatitis B surface antigen (HBsAg)	Drug screen
Hepatitis B surface antibody (anti-HBs)	Ethyl glucuronide (EtG)
Hepatitis B core total antibody (anti-HBc)	Other Serology
Hepatitis B core IgM antibody	Anti-nuclear antibody (ANA)
Hepatitis B core IgG antibody	Anti-smooth muscle antibody (ASMA) ^a
HBV DNA ^c	Anti-actin antibody ^b
Hepatitis C virus (HCV) testing:	Epstein-Barr virus (EBV) testing:
HCV antibody	EBV antibody
HCV RNA ^c	EBV DNA ^c
Hepatitis D virus (HDV) testing:	Cytomegalovirus (CMV) testing:
HDV antibody	CMV antibody
Hepatitis E virus (HEV) testing:	CMV DNA ^c
HEV IgG antibody	Herpes simplex virus (HSV) testing:
HEV IgM antibody	HSV (Type 1 and 2) antibody
HEV RNA ^c	HSV (Type 1 and 2) DNA ^c
Microbiology	Liver kidney microsomal type 1 (LKM-1) antibody
Culture:	
Blood	
Urine	

^a Not required if anti-actin antibody is tested.

^b Not required if anti-smooth muscle antibody (ASMA) is tested.

^c Reflex/confirmation dependent on regulatory requirements, testing availability, or both.

General Guidance for Venous Thromboembolic Events

VTE has been identified as an ADR for abemaciclib in combination with endocrine therapy. However, in studies with single-agent abemaciclib use in the metastatic breast cancer or other tumor types, including NSCLC, no increased rates of VTEs were observed as compared to the incidence of VTEs for these particular patient populations who were treated with other

anticancer agents. At this time, the mechanism underlying the association between abemaciclib and the occurrence of VTEs is not known. Venous thromboembolic events have been reported with other CDK4 and 6 inhibitors, and ET is known to be associated with the occurrence of VTEs. Monitor patients for signs and symptoms of deep vein thrombosis and pulmonary embolism and treat as medically appropriate.

Table 7: Dose Modification and Management — Venous Thromboembolic Events

CTCAE Grade	Abemaciclib Dose Modifications
Grade 1 or 2	No dose modification is required.
Grade 3 or 4	Suspend dose and treat as clinically indicated. Abemaciclib may be resumed when the patient is clinically stable.

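### Section 6, the VTE table and Section 7.3.6 give different dosing instructions for the same venous thromboembolic event, and no order of precedence is stated

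*Combined protocol and SAP*

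**What the plan says.** Three parts of the combined protocol and SAP can apply to a VTE.

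- **VTE guidance** (unnumbered heading after Table 7-4 in Section 7.3.4; its table is labelled Table 7). Grades 1 and 2 need no change. For Grade 3 or 4: "Suspend dose and treat as clinically indicated. Abemaciclib may be resumed when the patient is clinically stable". It gives neither a grade to be reached before resuming nor a dose at resumption.
- **Section 7.3.6 and Table 7-6.** The section heading is "General Guidance for Nonhematologic Toxicities (excluding diarrhea, increased ALT and ILD/Pneumonitis) Monitoring" and the table title reads "Nonhematologic Toxicities Excluding Diarrhea, ALT/AST Increased, and ILD/Pneumonitis". The lead-in to the bullets excludes diarrhea only. The table begins with "Grade 1 or 2 No dose modification is required". The next row covers "Persistent or recurrent Grade 2 toxicity that does not resolve with maximal supportive measures within 7 days to baseline or Grade 1", where the dose is suspended until baseline or Grade 1 and resumed one level lower. For severe events the bullet says "Grade 3 or 4: suspend dose until toxicity resolves to baseline or Grade 1. Resume at next lower dose".
- **Section 6, general guidelines,** for treatment-related toxicity other than pneumonitis. Tolerable Grade 2 may stay on the current dose. Intolerable Grade 2 is interrupted until Grade 1 or lower and then reduced. Grade 3 or 4 is interrupted until Grade 1 or lower, and treatment may then continue at a reduced dose. If the investigator considers a Grade 3 or 4 event life-threatening, treatment stops permanently.

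On creatinine, Section 7.3.2 reports that rises appeared in the first month, "remained elevated but stable through the treatment period, were reversible upon treatment discontinuation, and were not accompanied by changes in markers of renal function". It contains no dosing instruction.

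**The concern.** A catch-all rule that names its exceptions should name every event that has its own rule. Section 7.3.6 names diarrhea, ALT/AST and ILD/pneumonitis, but not VTE, although a VTE table precedes it in the same part of the protocol. A site that reads the exclusion list carefully can conclude that VTE falls under 7.3.6. A site that turns to the VTE table reaches a different instruction. Section 6 adds a third.

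What is at stake is consistency of exposure. The trial is multisite, plans 17 patients and assesses response at 8 (+/-4) weeks. Two patients with the same event could be resumed at different times and doses because their sites followed different pages.

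Creatinine raises a related but weaker question: 7.3.2 describes a persistent on-treatment rise without saying what to do about dose, so the catch-all is the only table left that could apply.

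**Working it through.** The plan gives no figure to reproduce here. The check sets the rules side by side.

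**Step 1. VTE, by grade**

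| VTE | VTE table | 7.3.6 / Table 7-6 | Section 6 (treatment-related only) |
|---|---|---|---|
| Grade 1 | No change | No change | May continue at current dose |
| Persistent or recurrent Grade 2, not settled in 7 days | No change | Suspend to baseline or Grade 1; next lower dose | Tolerable: may continue. Intolerable: interrupt to Grade 1 or lower, then reduce |
| Grade 3-4, not life-threatening | Suspend, treat; may resume when stable; dose not stated | Suspend to baseline or Grade 1; next lower dose | Interrupt to Grade 1 or lower; may continue after reduction |
| Grade 3-4, life-threatening | As the row above | As the row above | Discontinue permanently |

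The columns agree for Grade 1 and diverge in every lower row. In the Table 7-6 text as extracted, the Grade 3 or 4 row has no instruction beside it. This looks like a merged cell and is not counted as an error, because the bullets state the rule.

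**Step 2. Is precedence stated?** No. Section 7.3.4 says Table 7-3 is to be followed and Section 7.3.5 says Table 7-5 must be used. The VTE text has no such sentence, and neither Section 6 nor 7.3.6 says which yields.

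**Step 3. What turns on the choice.** Section 7.3.1 sets 50 mg steps. One step is 150/200 = 0.75, a 25% lower dose. Section 6 ends treatment for interruptions beyond 2 cycles, 2 x 28 = 56 days. A patient who is clinically stable, but not back to baseline or Grade 1 by then, could have resumed under the VTE table yet would pass that limit under 7.3.6.

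**Step 4. Scope wording inside 7.3.6.** The heading and table title exclude three categories; the bullet lead-in excludes one. Read alone, the bullets would cover Grade 3-4 ILD/pneumonitis, for which Table 7-2 says to discontinue. The heading guards against that reading, but the two should match.

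**Step 5. Creatinine, conditionally.**
- Grade 1, or Grade 2 that is neither persistent nor recurrent: 7.3.6 asks for no change, so there is no conflict.
- If a rise is treated as a toxicity and reaches Grade 2, then on 7.3.2's description it would not settle within 7 days on drug. Read literally, 7.3.6 then calls for suspension and reduction, as it does for Grade 3-4. Section 6 lets tolerable Grade 2 continue.
- Section 7.3.2 gives no grade, no frequency and no dosing instruction, so the documents do not show how often this arises.

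**The case against.** The strongest reply is that a dedicated table is normally read as governing over a general one, so a site would follow the VTE table. That is reasonable, and it rules out an inference a reader might draw, namely that 7.3.6 overrides the VTE table. No text gives 7.3.6 that status. But 7.3.6 does not rely on the convention: it lists its exceptions by name and omits VTE. The convention also has to be applied against Section 6, including its rule for life-threatening events.

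A reader might also infer that the VTE table forbids a dose reduction, making the two rules opposites. It does not. It is silent on dose, and elsewhere (Grade 2 diarrhea in Table 7-1, first Grade 3 in Table 7-5) the protocol says explicitly when no reduction is needed. The clear differences at Grade 3-4 are the recovery threshold and whether a reduction is specified. For persistent or recurrent Grade 2, the VTE table and 7.3.6 do conflict outright.

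The VTE guidance also reports no increased VTE rates with single-agent use compared with other anticancer agents. The situation may therefore be uncommon, and a site might judge a VTE unrelated, which takes Section 6 out. The conflict between the other two texts remains.

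On creatinine the objection largely succeeds. It is tempting to say the plan orders hold-and-reduce for a harmless laboratory effect. That needs a grade 7.3.2 does not give and a decision to treat the rise as a toxicity. Sections 7.4 and 9.1.4.7 make a laboratory change an adverse event only under conditions such as clinical significance, and Section 6 lets tolerable Grade 2 continue. Harmless is also an inference; 7.3.2 says glomerular function is unaffected and the rise reverses off drug. What stands is a gap, not a contradiction.

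**Conclusion.** Wrong as written: an internal contradiction. Sites cannot follow all three texts for a Grade 3-4 treatment-related VTE, or both the VTE table and 7.3.6 for a persistent or recurrent Grade 2 VTE. The mismatch between the 7.3.6 heading and its bullet lead-in is a separate, smaller error of the same kind. The creatinine point is secondary and holds only under the conditions in the working.

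The size is limited to inconsistent handling of the same event across sites, by at least one 25% dose step where the rules diverge on dose. A reader might go further and infer repeated reductions to half dose for recurring creatinine rises, or a measurable loss of the trial's ability to show activity. The documents support neither. They say nothing about rechallenge at a lower dose, give no frequency for VTE or for graded creatinine rises in this population, and offer no link from dose to response rate. The stated alpha, power and sample size are untouched.

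**What to change.** Reconcile Section 6, Section 7.3.2, the VTE table and Section 7.3.6/Table 7-6 so that each event has one governing rule. Either a complete scope statement or an explicit order of precedence would do this, and it must cover Section 6 as well as the tables. State in 7.3.2 which dosing instruction, if any, applies to a creatinine rise. Align the 7.3.6 bullet lead-in with its section heading and table title. Which clinical rule governs is for the sponsor to decide; this review does not propose one.

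The cost is wording, handled as a protocol modification with the IRB approval that Section 11.2 requires. It needs no extra tests or patients and no change to the analysis.

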7.3.7 Guidelines for monitoring pneumonitis

Monitor patients for pulmonary symptoms indicative of pneumonitis. In addition, withhold study therapy for acute onset of new or progressive unexplained pulmonary symptoms, such as dyspnea, cough and fever and during diagnostic workup for pneumonitis/ILD.

7.4 Adverse Event Reporting

For guidance on reporting adverse events, refer to the [Adverse Event SOP](#). Please modify the below template language as needed.

Adverse events will be graded according to CTCAE v5. Both Serious and Non-Serious Adverse Events will be clearly noted in source documentation and listed on study specific Case Report Forms (CRFs). The Protocol Director (PD) or designee will assess each Adverse Event (AE) to determine whether it is unexpected according to the Informed Consent, Protocol Document, or Investigator's Brochure, and related to the investigation. All Serious Adverse Events (SAEs) will be tracked until resolution, or until 30 after the last dose of the

study treatment.

SAEs CTCAE Grade 3 and above, and all subsequent follow-up reports will be reported to the Stanford Cancer Institute Data and Safety Monitoring Committee (DSMC) using the study specific CRF regardless of the event's relatedness to the investigation. It is the Investigator and study team's responsibility to report events meeting the IRB definition of 'Unanticipated Problem' to the IRB using eProtocol within 10 working days, or within 5 working days for deaths or life-threatening experiences.

No specific safety precautions or adverse event reporting guidance is required to the manufacturer. Follow standard precautions and reporting as below. Additional information is available in the Package Insert: https://www.accessdata.fda.gov/drugsatfda_docs/label/2017/208716s000lbl.pdf

For other participating sub-sites, non-serious grade 1 and 2 adverse events will be reported to the participating sites in regular conference calls. All adverse and serious adverse events should be recorded into the RedCap eCRF. All Serious Adverse Events (Grade 3 or above as graded by CTCAE v 5) will additionally be reported to the overall PI of the study at Stanford in writing within 24 hours of learning the event and to [contact]. The participating sub-site will also report to Eli Lilly as described at the end of this section. Stanford will promptly report SAEs to CCTO for forwarding as necessary to the Stanford IRB and DSMC; the participating sub-site will notify their IRB per their SOP. Any death associated with the use of investigational agents or devices will prompt suspension of further patient enrollment into the trial from all sites until the cause of death is investigated by the principal investigator from the respective site and the overall PI of the study at Stanford.

Regulatory and reporting requirements

It is the responsibility of the investigator to document all adverse events which occur during the investigation. An adverse event is any untoward medical occurrence in a patient or clinical investigation subject, temporally associated with the use of the medicinal product, whether or not considered related to the medicinal product. *An AE can therefore be any unfavorable and unintended sign (including an abnormal laboratory finding), symptom, or disease (new or exacerbated) temporally associated with the use of a medicinal product.* Anticipated day-to-day fluctuations of the disease under study that do not represent a clinically significant exacerbation or worsening need not be considered an adverse event.

In addition, any SAEs which occur as a result of protocol specific diagnostic procedures or interventions must also be reported.

(a) *Definition of Serious Adverse Events*

A serious adverse experience is any event which is fatal, life threatening, disabling or incapacitating or results in hospitalization, prolongs a hospital stay or is associated with congenital abnormality. In addition, any experience which the investigator regards as serious or which would suggest any significant hazard, contraindication, side effect or precaution that may be associated with the use of the drug should be reported as a serious adverse event. Examples of such events are invasive or malignant cancers, intensive treatment in an emergency room or at home for allergic bronchospasm, blood dyscrasias or convulsions that do not result in hospitalization, or development of drug dependency or drug abuse.

Abnormal laboratory findings (e.g., clinical chemistry, hematology) or other abnormal assessments (e.g., x-rays, scans, vital signs, etc.) that are judged by the investigator as **clinically significant** will be recorded as AEs or SAEs if they meet the definition of an AE or SAE.

Life threatening definition:

An adverse event is life threatening if the patient was at immediate risk of death from the event as it occurred (i.e. it does not include a reaction that if it had occurred in a more serious form might have caused death). For example, drug-induced hepatitis that resolved without evidence of hepatic failure would not be considered life threatening even though drug-induced hepatitis could be fatal.

Disability/incapacitating definition:

An adverse experience is incapacitating or disabling if the experience results in a substantial and/or permanent disruption of the patient's ability to carry out normal life functions.

Hospitalization definition:

An adverse event that results in emergency department admission greater than 24 hours or requires general in-patient hospitalization. Hospitalization for elective treatment of a pre-existing condition that did not worsen from baseline is not considered an AE.

Reporting Serious Adverse Events

Any serious adverse events that occur during the clinical study and up to 30 days after completion of all study treatments must be reported by the investigators as study-related SAE. Attribution of SAE to study drug should follow the standard attribution and grading system as specified by CTEP (<http://ctep.cancer.gov/reporting/adeers.html>, see table below).

Note: During the screening period, only protocol-related SAE's will be reported. Documentation for non-protocol related events will be provided in patient chart.

Attribution of Adverse Events:

Code	Descriptor	Definition
1	Unrelated	The Adverse Event is clearly not related to the investigational agent(s)
2	Unlikely	The Adverse Event is doubtfully related to the investigational agent(s)
3	Possible	The Adverse Event may be related to the investigational agent(s)
4	Probable	The Adverse Event is likely related to the investigational agent(s)
5	Definite	The Adverse Event is clearly related to the investigational agent(s)

In addition, any SAEs which occur as a result of protocol specific diagnostic procedures or interventions must also be reported to the local DSMB and local IRB (using the formed attached or an allowable local form), the coordinating site (Stanford University).

SAEs

Serious Adverse Event Reporting to Lilly:

- To comply with applicable laws, regulations and standards regarding Investigators' and Institution's obligations, as the sponsor of the Study, to collect and report adverse events to regulatory authorities, IRBs, Ethics Committees or other third parties. In addition to the obligations set forth below, Investigators and Institutions agree to provide Lilly with a copy of all information Investigator and/or Institution submit to regulators related to any adverse events for the Study Drug that occur during the Study that Investigator and/or Institution have not otherwise provided Lilly;
- To notify Lilly, sub-investigators, and the IRB of any problems involving risk to Study patients and report new safety information to IRBs in accordance with applicable requirements;
- to notify Lilly within fifteen (15) business days of Investigator and/or Institution receiving notification of any "serious" adverse event experienced by a patient participating in the Study and receiving Study Drug. For purposes of this requirement, "serious" means: (1) death; (2) in-patient hospitalization or prolonged hospitalization; (3) life-threatening; (4) persistent or significant disability or incapacity; (5) congenital anomaly or birth defect; or (6) other serious events that may jeopardize the patient and may require medical or surgical intervention to prevent one of the other five listed outcomes. Serious adverse events should be reported to Lilly using a CIOMS Form or other form acceptable to Lilly. Investigator and Institution further agree to make available promptly to Lilly such records as may be necessary and pertinent for Lilly to further investigate an adverse event in the Study that is possibly associated with the Study Drug.

8. CORRELATIVE/SPECIAL STUDIES

No study specific correlative procedures are planned. Analysis of exploratory biomarkers will utilize data derived from standard of care testing platforms.

9. STUDY CALENDAR

Table 9-1 Visit evaluation Schedule		Screening / Baseline	Day 1 of Cycle 1 (28d) +/- 3	Day 1 of Cycle 2 (28d) +/- 3	Day 1 of Subsequent cycles (28d) +/- 3	Day 1 of study treatment (EoT) (at last visit, or up to 30 days from last dose)
Visit Number	1	2	3	4, 5..		Last
Day of cycle	D-30 to -1	D1	D29	D57, D85..		Last
Obtain Informed Consent	X					
Patient history						
Inclusion/exclusion criteria	X					
Diagnosis and extent of cancer	X					
Demography	X					
Relevant medical history/current medical conditions	X					
Prior antineoplastic therapy (meds, surgery, radiation)	X					
Prior/concomitant medications	X	X	X	X	X	X
Surgical and Medical Procedures	X	X	X	X	X	X
Physical examination						
Performance status (WHO)	X	X	X	X	X	X
Height	X					
Weight	X	X	X	X	X	X
Vital signs	X	X	X	X	X	X

Table 9-1. Visit evaluation Schedule (continued)		Screening / Baseline	Day 1 of Cycle 1 (28d) +/- 3	Day 1 of Cycle 2 (28d) +/- 3	Day 1 of Subsequent cycles (28d) +/- 3	End of study treatment (EoT) (at last visit, or up to 30 days from last dose)
Visit Number	1	2		3	4, 5,...	Last
Day of cycle	D-30 to-1	D1		D29	D57, D85..	Last
Lab assessments*	X	X		X	X	X
CBC	X	X and at cycle 1 d14		X and at cycle 2 d14	X	X
Chemistry	X	X and at cycle 1 d14		X and at cycle 2 d14	X	X
Creatinine clearance	X					
Serum Pregnancy test for women of childbearing potential	X (-7 to -1 days)					
Imaging						
Standard of care imaging of neck/neck/abdomen/pelvis (CT, MRI) as indicated to areas of known/ suspected disease	X				X (within 0-7d prior to every odd cycle)	
Standard of Care Imaging of the brain at baseline and then as clinically indicated (MRI/CT)	X				X (if known or suspected brain metastases)	
Safety						
Adverse Events	X	X	X	X	X	X
ECG	X					
Drug administration			Continuous			

*Please refer to Table 9-3 for local Clinical laboratory parameters

